10.1.9 Source Documents

Source documents provide evidence for the existence of the participant and substantiate the integrity of the data collected. The investigator/institution should maintain adequate and accurate source documents and study records that include all pertinent observations on each of the site's participants. Source documents and data should be attributable, legible, contemporaneous, original, accurate, and complete. Changes to source data should be traceable, should not obscure the original entry, and should be explained if necessary (eg, via an audit trail). Source documents are filed at the investigator's site.

Data reported on the CRF or entered in the eCRF that are transcribed from source documents must be consistent with the source documents or the discrepancies must be explained. The investigator/institution may need to request previous medical records or transfer records, depending on the study. Also, current medical records must be available.

10.1.10 Study and Site Closure

The Sponsor or its designee may stop the study or study-site participation in the study for medical, safety, regulatory, administrative, or other reasons consistent with applicable laws, regulations, and GCP.

In the event the Sponsor prematurely terminates a particular study site, the Sponsor or designee will promptly notify that study site's IRB/IEC as specified by applicable regulatory requirement(s).

10.2 Appendix 2: Clinical Laboratory Tests

- The tests detailed in Table 11 will be performed by the central laboratory. (Note: Local laboratory assessment of protocol-required safety laboratory assessments [chemistry, hematology, and pregnancy] may be permissible under extenuating circumstances. Sponsor approval must be obtained, and results must be recorded in the appropriate eCRF).
- Documentation of the index's first detectable SARS-CoV-2 local laboratory test result from a sample collected within 5 days prior to randomization of the potential participant(s) in the study is required.
- Other local laboratory results are only required if the central laboratory results are not available in time for participant management, or for either study intervention administration and/or response evaluation. If a collection of a local sample is required, it is important that the sample for central analysis is obtained first (eg, NP swab). Additionally, if the local laboratory results are used for participant management, or to make either a study intervention decision or response evaluation, the results must be entered into the eCRF.
- Protocol-specific requirements for inclusion or exclusion of participants are detailed in Section 5 of the protocol.
- Additional tests may be performed at any time during the study as determined necessary by the investigator or required by local regulations.
- The investigator (or medically qualified designee) must document their review of each laboratory safety report (eg, hematology, chemistry, pregnancy).
- Laboratory/analyte results that could unblind the participant's intervention group will not be reported to blinded site and Sponsor personnel. These laboratory results include, but may not be limited to virology results with the exception of screening results and error reports.

Laboratory Assessments	Parameters		
Hematology	Platelet Count	RBC Indices:	WBC count with Differential:
	RBC Count	MCV	Neutrophils
	Hemoglobin	MCH	Lymphocytes
	Hematocrit	RDW	Monocytes
			Eosinophils
			Basophils
			Calculation of:
			Neutrophil/lymphocyte ratio
			Absolute Neutrophil Count
Chemistry	BUN	Chloride	AST/SGOT
	Albumin	Calcium	ALT/SGPT
	Creatinine	Phosphorous	Alkaline phosphatase
	Glucose	Amylase	GGT
	(nonfasting)		
	Potassium	Lipase	LDH
	Bicarbonate	Total Protein	Total bilirubin (and direct bilirubin if
			total bilirubin is elevated above the
			ULN)
	Sodium	Magnesium	
	СК		
Pregnancy Testing	Urine or Serum	hCG pregnancy test (as n	needed for WOCBP)
Serology	SARS-CoV-2 A	ntibodies	
Virology	• SARS-CoV-2 R	NA (RT-PCR; qualitative	e and quantitative) from NP swab samples
	• SARS-CoV-2 G	ene Sequencing	
Other Laboratory	Testing for othe	r respiratory pathogens is	s planned from NP swab samples.
Assessments			
			lood urea nitrogen; CK=creatine kinase;
GGT=gamma-glutamyl transferase; hCG=human chorionic gonadotropin; LDH=lactate dehydrogenase; MCH=mean			
corpuscular hemoglobin; MCV=mean corpuscular volume; NP=nasopharyngeal; RBC=red blood cell; RDW=red cell distribution width; RNA=ribonucleic acid; RT-PCR=reverse transcription polymerase chain reaction;			
			polymerase chain reaction; erum glutamic-oxaloacetic transaminase;
			; WBC=white blood cell; WOCBP=women of
childbearing potential		obi apper mint or normal,	

Study Period:	Screening	Interve	ention		Follow-up			
Visit Number/Name:	1	2	3	4	5	6	COVID 10	
Scheduled Day (Window)	(≤5 days prior to rand)	Day 1	Day 5 (+ 2 days) EOT	Day 14 (+3 days)	Day 21 (+3 days)	Day 29 (+3 days) LFU	COVID-19 Confirmation Visit	Total Blood Volume
Laboratory Assessment								
Chemistry ^a (Day 14 includes serum pregnancy)	Per Local Requirements	2.5	2.5	2.5	N/A	N/A	N/A	10.0
Hematology ^a	N/A	2.0	2.0	2.0	N/A	N/A	N/A	8.0
Anti-SARS-CoV-2 Antibody Serology Testing	N/A	5.0	N/A	5.0	N/A	5.0	N/A	15.0
Total	N/A	9.5	4.5	9.5	N/A	5.0	N/A	33.0
COVID-19=coronavirus infectious disea			l Af last study inte	I ervention dose	I)∙ I F∐=I ate F	Follow-Un· N/A:	=not applicable: SA	

COVID-19=coronavirus infectious disease 2019; EOT=end of treatment (day of last study intervention dose); LFU=Late Follow-Up; N/A=not applicable; SARS-CoV-2=severe acute respiratory syndrome coronavirus 2

^a Where local safety laboratories are permitted on days other than screening (see Appendix 2), volumes will be per local requirements.

10.3 Appendix 3: Adverse Events: Definitions and Procedures for Recording, Evaluating, Follow-up, and Reporting

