NP Swabs ^f for Viral Testing/Quantification		Х	Х	Х		Х	Х	 NP swabs at the Day 1, Day 5, Day 14, and Day 29 visits should be collected from all participants. NP swabs for confirmation of COVID-19 should be collected from all participants who develop qualifying symptoms of COVID-19 through Day 29. NP swab must be collected by site personnel or medically qualified designee. If an additional sample is collected for testing per local guidelines, the swab sample for central laboratory testing should be collected first.

Study Period:	Screening	Inter	vention		Fo	llow-up	Notes	
Visit Number/Name:	1 ^{a,b}	2 ^{a,b}	3	4	5	6	COVID-19 Confirmation Visit ^c	
Scheduled Day (Window)	(≤5 days prior to rand)	Day 1	Day 5 (+2 days) EOT	Day 14 (+3 days)	Day 21 (+3 days)	Day 29 (+3 days) LFU		
Type of Visit	C ^d	C ^d	C d	C ^d	V ^e	C ^d	C ^d	C = Clinic Visit V = Virtual Visit
Prophylaxis Outcome Assessment				Х		Х	Х	Assess for all participants whether a clinical success (no laboratory-confirmed COVID-19), failure (laboratory-confirmed COVID-19), or indeterminate. At the COVID-19 Confirmation Visit, assess only for participants who develop laboratory-confirmed COVID- 19 with symptoms. See Section 8.2.6.
Hospitalization Status			Х	Х	Х	Х		Collect from all participants.
Survival Status						Х		Collect from all participants.
Health care Utilization for COVID-19			X	Х	Х	Х	Х	Collect only from participants with laboratory-confirmed COVID-19.
Assessment for Severity of COVID-19 (NIAID Scale)			X	Х	Х	X	х	Collect only from participants with laboratory-confirmed COVID-19.
EuroQoL EQ-5D-5L Questionnaire		Х	X	Х		Х		Collect from all participants.
Safety Procedures								
Directed Physical Examination	Х	Х	Х				Х	Including height and weight at screening only
Vital Signs	Х	Х	Х	Х			Х	Heart rate, blood pressure, respiratory rate, temperature.

Study Period:	Screening	Inter	vention		Fo	llow-up	Notes	
Visit Number/Name:	1 ^{a,b}	2 ^{a,b}	3	4	5	6	COVID-19 Confirmation Visit ^c	
Scheduled Day (Window)	(≤5 days prior to rand)	Day 1	Day 5 (+2 days) EOT	Day 14 (+3 days)	Day 21 (+3 days)	Day 29 (+3 days) LFU		
Type of Visit	C ^d	C ^d	C ^d	C ^d	V ^e	C ^d	C ^d	C = Clinic Visit V = Virtual Visit
Blood Collection for Local Laboratory Evaluation	X ^g							

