4.2.1 Rationale for Endpoints

4.2.1.1 Efficacy Endpoints

The primary efficacy endpoint for the study, COVID-19 (laboratory-confirmed SARS-CoV-2 infection with symptoms), was selected in accordance with the US FDA guidance on development of drug and biological products for treatment or prevention of COVID-19 [Food and Drug Administration 2021]. Development of symptomatic disease represents a clinically meaningful endpoint for participants since it demonstrates the onset of deleterious effects they can directly perceive. A COVID-19 case for the study is defined as a participant with qualifying symptoms of COVID-19 with onset through Day 14 (for the primary endpoint) and SARS-CoV-2 detected by central laboratory RT-PCR testing from a sample collected at the COVID-19 Confirmation Visit. Laboratory-confirmed COVID-19 with onset through Day 29 will also be assessed as an exploratory endpoint. The onset of COVID-19 is determined by the day of onset of symptoms, rather than the day of the COVID-19 Confirmation Visit. Therefore, the day of onset of COVID-19 symptoms supports the primary endpoint, even if the day of the COVID-19 Confirmation Visit is later than Day 14. The qualifying symptoms of COVID-19 are provided in Section 8.2.2.

The study will evaluate SARS-CoV-2 RNA as a secondary endpoint through Day 14 (and as an exploratory endpoint through Day 29) to assess the impact of MOV on preventing viral transmission in participants with undetectable SARS-CoV-2 in baseline NP swabs. Viral transmission, even in the absence of symptoms, represents an important outcome with regards to infection control. This is best evaluated via RT-PCR detection of SARS-CoV-2 RNA since nucleic acid amplification offers the most sensitive method for assessment of viral transmission. For this reason, SARS-CoV-2 RNA has been selected as the appropriate endpoint.

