6.3.3 Blinding

A double-blinding technique with in-house blinding will be used. MOV and placebo capsules are identical in appearance and will be packaged identically so that the blind is maintained. The participant, the investigator, and Sponsor personnel or delegate(s) who are involved in the study intervention administration or clinical evaluation of the participants are unaware of the intervention assignments.

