8.2.6 Assessment of Prophylaxis Outcome

The clinical outcome of prophylaxis will be assessed at the Day 14 and Day 29 visits for all participants and at the COVID-19 Confirmation Visit for participants who develop laboratory-confirmed COVID-19 with symptoms (see Section 1.3.1). Assessments should be made according to the following definitions:

Term	Definition		
Clinical Success	The participant does not develop laboratory-confirmed COVID-19 with onset within the window of interest (ie, symptom onset on or before Day 14 for the Visit 4 assessment; and on or before Day 29 for Visit 6 assessment).		
	Note: Participants who remain asymptomatic through Day 14 (or Day 29, for the Day 29 endpoint) are also considered clinical successes regardless of SARS-CoV-2 results (positive, negative, or missing).		
Clinical Failure	The participant develops laboratory-confirmed COVID-19 with onset within the window of interest (ie, symptom onset on or before Day 14 for the Visit 4 assessment; and on or before Day 29 for Visit 6 assessment).		
	The date of onset is considered the date of onset of symptoms. Note: An assessment of "Clinical Failure" on or before Day 14/Visit 4 will also be carried forward to the Day 29/Visit 6 assessment.		
Indeterminate	The outcome is indeterminate if any of the following apply:		
	• The participant is lost to follow-up during or has discontinued from the study prior to the window of interest (ie, prior to Visit 4 or Visit 6 for the outcome assessments conducted at those visits).		
	Note: This definition does not apply to participants who developed laboratory-confirmed COVID-19 with symptoms prior to leaving the study. For those participants, prophylaxis outcome should be assessed as "Clinical Failure" per the definition above.		
	• Death unrelated to COVID-19.		
	• The participant is symptomatic and missing the required viral test for confirmation of COVID-19.		
	Note: A virus-detectable NP swab collected within +/-5 days of symptom onset is considered to be within an acceptable window to confirm onset of COVID-19. A virus-undetectable NP swab that is collected within 5 days after symptom onset is considered to be within an acceptable window to rule out COVID-19.		
	NP swabs collected outside these windows are considered missing.		
	• There are other extenuating circumstances that preclude classification as a clinical success or failure, such as:		

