Moreover, a participant without a Day 14 clinical outcome assessment, but assessed as a clinical success through Day 29 will be treated as a clinical success through Day 14. A participant without a Day 29 clinical outcome assessment, but assessed as a clinical failure through Day 14 will be treated as a clinical failure through Day 29. If a participant discontinued from the study prior to the Day 14 or the Day 29 visit, but was assessed as a clinical failure from the COVID-19 Confirmation Visit, then the clinical failure should be carried forward to the Day 14 and/or the Day 29 visit after the COVID-19 Confirmation Visit. All other missing clinical outcome assessments will be imputed as clinical failures.

For the evaluation of the secondary hypothesis, the superiority of MOV compared with placebo with respect to the percentage of participants (regardless of SARS-CoV-2 results in baseline NP swabs) developing COVID-19 by Day 14 will be assessed using the same method in the primary hypothesis, ie, the stratified Miettinen and Nurminen method with CMH weights [Miettinen, O. and Nurminen, M. 1985] (stratified by age and household size as described in Section 6.3.2, and SARS-CoV-2 status in baseline NP swab). The secondary hypothesis will be evaluated by testing the null hypothesis $p_{ts} \ge p_{cs}$ versus the alternative hypothesis $p_{ts} < p_{cs}$, where p_{ts} and p_{cs} refer to event rates (percentages of participants developing COVID-19 by Day 14) in MOV and placebo groups, respectively. The null hypothesis will be rejected if the 1-sided p-value is less than 0.0249 (see Section 9.8 for alpha adjustment) and the superiority of MOV relative to placebo will be concluded for this secondary endpoint.

The efficacy of MOV compared with placebo for the prevention of COVID-19 with respect to the percentage of participants with undetectable SARS-CoV-2 in baseline NP swabs developing COVID-19 through Day 29 will be evaluated. The difference in percentages between treatment groups (MOV minus placebo) and the associated 95% CI will be

MK-4482-013-05 FINAL PROTOCOL

16-OCT-2022

calculated using the stratified Miettinen and Nurminen method with CMH weights [Miettinen, O. and Nurminen, M. 1985] (stratified by age and household size as described in Section 6.3.2).

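### Sites must restrict follow-up severity and health care utilization data to laboratory-confirmed cases, and call outcomes for symptomatic participants, without the RT-PCR result that confirms a case

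*Combined protocol and SAP*

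**What the plan says.** **What is withheld.** Appendix 2 (Section 10.2) states: "Laboratory/analyte results that could unblind the participant's intervention group will not be reported to blinded site and Sponsor personnel". It continues: "These laboratory results include, but may not be limited to virology results with the exception of screening results and error reports". Section 6.3.3 lists those kept unaware of assignment: "The participant, the investigator, and Sponsor personnel or delegate(s) who are involved in the study intervention administration" or clinical evaluation. The synopsis records no clinical adjudication committee.

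**What must be classified.** Section 8.2.6: "The clinical outcome of prophylaxis will be assessed at the Day 14 and Day 29 visits for all participants", and also at the Confirmation Visit for those who prove to be confirmed cases. The Schedule of Activities (1.3.1) adds: "Assess for all participants whether a clinical success (no laboratory-confirmed COVID-19), failure (laboratory-confirmed COVID-19), or indeterminate". Section 4.2.1.1 defines a case as qualifying symptoms plus "SARS-CoV-2 detected by central laboratory RT-PCR testing from a sample collected at the COVID-19 Confirmation Visit".

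**What is collected only from cases.** For both health care utilization and NIAID severity, the Schedule of Activities says: "Collect only from participants with laboratory-confirmed COVID-19". Sections 8.2.9 and 8.2.10 repeat the restriction.

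**What the analysis does.** Section 8.2.5 names central RT-PCR as the source for efficacy, with local results only in extenuating circumstances and OP swabs only where no NP result exists. Table 4 counts indeterminate outcomes as cases. Section 9.6.1 then adds: "All other missing clinical outcome assessments will be imputed as clinical failures".

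**The concern.** Case status is defined by a central laboratory result, but the people told to act on case status are not given that result. Two things follow.

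First, a site cannot tell which symptomatic participants belong in the health care utilization and follow-up severity collection. Data not collected at the visit may not be recoverable later. The gaps would also track local testing practice rather than anything planned.

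Second, the SAP refers to a clinical outcome assessment as a data item and imputes it when absent. It does not say whether that item is the visit entry or a status derived from central RT-PCR. The two can differ for a symptomatic participant whose central result was never shown to the site.

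**Working it through.** The plan gives no figure on this point, so the check is mainly a comparison of text.

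**1. Does any exception release the confirming result?** Section 8.2.4 schedules participants' swabs at Days 1, 5, 14 and 29 and at the Confirmation Visit. Only index cases have a swab labelled as screening. Table 11 lists qualitative as well as quantitative RT-PCR under virology. At most, the screening exception might be stretched to the Day 1 swab. It does not reach a Confirmation Visit swab.

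**2. Who is affected?**

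| Participant | Viral result needed for the outcome call? | What the site holds |
|---|---|---|
| Asymptomatic throughout the window | No; 8.2.6 makes this a success whatever the RT-PCR result | Enough |
| Symptomatic, local test done | Yes | A local result, usable for a working call |
| Symptomatic, no local test | Yes | Symptoms only |

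The conflict is confined to symptomatic participants and is sharpest in the last row. Section 8.2.3 treats a local sample at the Confirmation Visit as optional. Appendix 2 calls for local results when central ones are not available in time for response evaluation. Section 8.2.5 admits them to the efficacy analysis only in extenuating circumstances. These three statements do not line up.

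**3. What could be lost?**
- *NIAID severity.* Section 8.2.3 already includes a severity assessment at every Confirmation Visit. Hospitalization and survival are collected from everyone, and 8.2.7 records oxygen use and ventilation in hospital, so levels 3 to 8 could largely be rebuilt. Ability to carry out usual activities, which bears on levels 1 and 2, is assessed for all at Days 1, 5, 14 and 29 and the Confirmation Visit. It is not assessed at Day 21, where severity is also due.
- *Health care utilization.* Section 4.1 counts telemedicine, office, urgent care and emergency visits as well as hospitalization. Only hospitalization (24 hours or more, Section 8.2.7) is a scheduled item for everyone. Section 8.2.3 asks for records when symptoms were assessed elsewhere, which helps in part. Use short of hospitalization is the most exposed item.

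**4. How many participants does the collection rule concern?** Inputs are from Sections 9.9.1 and 9.9.2, equal allocation: 550 undetectable and 138 detectable at baseline per group; attack rates 8% and 3.2% (undetectable, placebo and MOV) and 40% and 28% (detectable).
- Placebo: 550 × 0.08 + 138 × 0.40 = 44.0 + 55.2 = 99.2
- MOV: 550 × 0.032 + 138 × 0.28 = 17.6 + 38.6 = 56.2
- Total: about 155 cases by Day 14

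This is the number for whom the items are due, not the number who would lose them. The documents give no local-testing rate.

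**5. What does the imputation text do with a withheld result?** Section 8.2.6 treats a swab as missing when it falls outside the timing windows, and Table 4 points back to those windows. An in-window swab, tested centrally and not shown to the site, is therefore not a missing test. However, the last rule in 9.6.1 speaks of missing outcome assessments, not missing tests. If a site left the Day 14 entry blank for a symptomatic, RT-PCR-negative participant, 8.2.6 read with 8.2.5 gives success, while the last rule of 9.6.1, read literally, gives failure. Section 9.5.1 also excludes indeterminate outcomes from the Per-Protocol population and ties the Ukraine exclusion to the absence of the Day 14 assessment, so the source matters for populations too.

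**The case against.** The strongest reply is that the documents already identify the source. Section 4.2.1.1 defines a case by central RT-PCR, 8.2.5 uses central RT-PCR for efficacy, and 9.4.1 defines the endpoint as laboratory-confirmed infection with symptoms rather than a rating. Sections 1.3.1 and 8.2.6 do not name the assessor. Local results give sites a working route, and Confirmation Visit severity is collected before any result is known. The items restricted to cases serve exploratory objectives only. All of this stands, and it limits the point.

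It does not remove the point. Central derivation cannot restore health care use that was not asked about, and 8.2.9 gives that judgement to the investigator or a designee. Nor does any section state the derivation or say which source prevails when it differs from the visit entry.

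A reader might go further and infer a loss of power, with symptomatic non-cases marked indeterminate and imputed as cases. Suppose a share q of non-cases in each arm were so treated, at 550 per group and one-sided 0.0249. The rates become 0.08 + 0.92q and 0.032 + 0.968q. At q = 0 the normal approximation gives about 93%, matching Table 7. At q = 5% (12.6% v 8.04%) it gives 70%, and at q = 10% (17.2% v 12.88%) it gives 52%. These figures are purely conditional. The documents give no value for q, and no section lets a site's lack of access override an available central result.

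**Conclusion.** The conflict between Appendix 2 and the case-restricted collection rule is real and should be corrected. It affects health care utilization most, follow-up NIAID severity less, and the outcome call only in symptomatic participants. About 155 participants would fall under the collection rule by Day 14 at the planning rates with equal allocation; the fraction with lost data is unknown.

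A reader might infer that the primary endpoint cannot be assessed as written. The documents do not support that: participants who stay asymptomatic are classified without virology, missing tests are defined by swab timing rather than disclosure, and central RT-PCR is the stated efficacy source. What remains for the primary analysis is an ambiguity in 9.6.1 that wording can close. This conclusion assumes that Appendix 2 is applied as written and that no companion document gives sites the qualitative result.

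**What to change.** 1. **Schedule of Activities, 8.2.9 and 8.2.10.** Collect health care utilization and NIAID severity from every participant with qualifying symptoms, and restrict to RT-PCR-confirmed cases at analysis. Cost: a few extra eCRF entries for participants who prove negative, for exploratory endpoints. No added participants, visits or swabs.

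2. **Sections 8.2.6 and 9.6.1, reconciled with Appendix 2.** State that:
   - viral confirmation for the Day 14 and Day 29 outcomes comes from central RT-PCR (local or OP results only as 8.2.5 allows) combined with symptom-onset dates;
   - a result withheld from the site is neither missing nor indeterminate for Table 4 or for the closing imputation rule;
   - the other indeterminate reasons (unrelated death, agents given other than as rescue, illness that cannot be told apart from another diagnosis) come from blinded eCRF data or from a named role with access to the results it needs.

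   RT-PCR and onset dates alone cannot supply that last group of reasons. The Per-Protocol population is fixed before final unblinding, so the chosen route must also work while the study team is blinded. Cost: wording, plus assigning that role if one is used.
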